8.12 Laboratory assessments

Adverse Events

A detailed definition for AEs is provided in (Section 13.1).

Concomitant Medication Use

Use of concomitant medications will be recorded according to the Visit schedule (Appendix 1).

Vital Signs

Vital sign measurements will be recorded according to the schedule specified in Appendix 1 and will include BP, HR, body temperature, weight, and height. Weight will be measured without shoes and having removed

all outdoor wear such as jackets, sweaters or sweatshirts and heavy pocket items. Height will be measured once during screening without shoes.

Physical Examination

A complete physical examination will be performed according to the schedule specified in Appendix 1.

The physical examination will include appearance, eyes, ears, nose, head, throat, neck, chest, lungs, heart, abdomen, extremities, skin, musculoskeletal system.

Electrocardiogram (ECG)

A 12-lead ECG will be performed according to the schedule specified in Appendix 1.

Initially, ECG output will be evaluated by the Investigator at time of performance (signed and dated) and the printout should be kept in the source documentation file. When potentially clinically significant findings are detected by the Investigator. All communications and diagnoses should be filed in the source documentation file.

The final decision as to whether or not the ECG findings are of clinical significance to the patient is the Investigator's responsibility.

Eastern Cooperative Oncology Group (ECOG) Performance Status

Evaluation of this 5-point scale will be performed according to the schedule specified in Appendix 1. The ECOG performance scale is used by doctors and researchers to assess how a patient's disease is progressing and assess how the disease affects the daily living abilities of the patient. The ECOG definitions are presented in Appendix 5.

Laboratory Assessments

All routine clinical laboratory assessments will be performed by a local laboratory according to the schedule specified in Appendix 1. The laboratory evaluations will include:

1. Hematology (CBC)
2. Coagulation
3. Serum biochemistry
4. Urine analysis
5. Pregnancy test for women of childbearing potential
6. Bone marrow aspirate (or bone marrow biopsy when needed)
7. Karyotype (if initially abnormal)

9 CRITERIA FOR MEASUREMENT OF STUDY ENDPOINTS

9.1 Efficacy Outcome Measures

Primary Endpoint:

For MDS patients:

Overall response rate (ORR), defined as the proportion of patients who achieve a CR or PR per proposal for modification of the International Working Group (IWG) criteria for MDS, 2006 (Appendix 11):

1. CR is defined as bone marrow blasts $\leq 5\%$, without persistent dysplasia will be noted with normal maturation of all cell lines peripheral blood: Hgb ≥ 11 g/dL platelets $\geq 100 \times 10^9/L$, ANC $\geq 1.0 \times 10^9/L$, blasts 0%.
2. PR is defined as all CR criteria if abnormal before treatment except for bone marrow blasts decreased by $\geq 50\%$ over pretreatment but still $> 5\%$ cellularity.

For AML patients:

CR Rate, defined as the proportion of patients who achieve a CR per the ELN2017 criteria: CR is defined as BM blasts $< 5\%$, absence of circulating blasts and blasts with Auer rods, absence of extramedullary disease, ANC $\geq 1.0 \times 10^9/L$ (1,000/ μ L); platelet count $\geq 100 \times 10^9/L$ (100,000/ μ L).

Secondary Endpoints:

For MDS patients:

1. Overall improvement rate (OIR), defined as the proportion of patients reaching a CR, Marrow CR, PR, or hematologic improvement (HI) per proposal for modification of the IWG criteria for MDS, 2006 (Appendix 11). Marrow CR is defined as bone marrow blasts $\leq 5\%$ and decreased by 50% over pretreatment. Peripheral blood: if HI responses, they will be noted in addition to marrow CR. HI is defined as:
 - a. Erythroid response (pretreatment, < 11 g/dL) is defined as Hgb increase by ≥ 1.5 g/dL. Relevant reduction of units of red blood cells (RBC) transfusions by an absolute number of at least 4 RBC transfusions/8 weeks, compared with the pretreatment transfusion number in the previous 8 weeks. Only RBC transfusions given for a Hgb of ≤ 9.0 g/dL will count in the RBC transfusion response evaluation.
 - b. Platelet response (pretreatment $< 100 \times 10^9/L$) is defined as absolute increase of $\geq 30 \times 10^9/L$ for patients starting with $> 20 \times 10^9/L$ platelets, and an increase from $< 20 \times 10^9/L$ to $> 20 \times 10^9/L$ and by at least 100%.
 - c. Neutrophil response (pretreatment, $< 1.0 \times 10^9/L$) is defined as at least 100% increase and an absolute increase $> 0.5 \times 10^9/L$

2. Duration of Response (DOR), defined as time from the date of the first observed PR/CR to the date of the first subsequent documented disease progression or relapse per IWG 2006 criteria, or death from any cause.
3. Progression Free Survival (PFS), for patients with at least a PR, defined as time from the date of the first dose of study treatment to the date of the first documented disease progression or relapse per IWG 2006 criteria, or death from any cause.
4. Overall Survival (OS), defined as time from the date of the first dose of study treatment to the date of death from any cause.
5. Event-Free Survival (EFS) defined as the number of days from the date of the first dose of study drug to the date of earliest disease progression or death of any cause.
6. Rate of bone marrow blast response, defined as the proportion of patients with a reduction in bone marrow blast counts following treatment.
7. Time to AML transformation, defined as time from first treatment dose to the first date in which AML is established.
8. CR Rate, defined as the proportion of participants who achieved a CR per the IWG 2006 Criteria.
9. Rate of HI, defined as the proportion of patients reaching a HI per the IWG 2006 Criteria.

For AML patients:

1. Overall response rate (ORR) including; CR and CRi according to the Diagnosis and Management of AML in Adults: 2017 ELN Recommendations from an International Expert Panel Revised (see Appendix 12) (Döhner et al., 2017)
 - a. CR is defined as bone marrow blasts < 5%; absence of circulating blasts and blasts with Auer rods; absence of extramedullary disease; ANC $\geq 1.0 \times 10^9/L$ (1000/ μ L); platelet count $\geq 100 \times 10^9/L$ (100 000/ μ L)
 - b. CRi is defined as all CR criteria except for residual neutropenia (< $1.0 \times 10^9/L$ (1,000/ μ L)) or thrombocytopenia (< $100 \times 10^9/L$ (100,000/ μ L)).
2. Duration of Response (DOR), defined as time from the date of the first observed CR/CRi to the date of the first subsequent documented disease progression or relapse per IWG 2006 criteria, or death from any cause.
3. Progression Free Survival (PFS) for patients with at least CRi, defined as time from the date of the first dose of study treatment to the date of the first documented disease progression or relapse per IWG 2006 criteria, or death from any cause.
4. Overall Survival (OS) defined as time from the date of the first dose of study treatment to the date of death from any cause.

5. Event-Free Survival (EFS) defined as the number of days from the date of the first dose of study drug to the date of earliest disease progression or death of any cause.
6. Rate of CR without Minimal Residual Disease (CR-MRD-), defined as the proportion of patients reaching a CR with BM blast negativity by multi-color flow cytometry.
7. Time to neutrophil recovery in patients with CR or PR, defined as:
 - a. Number of days from Day 1 of commencing induction therapy to first day of neutrophils $0.5 \times 10^9/L$
 - b. Number of days from Day 1 of commencing induction therapy to first day of neutrophils $1 \times 10^9/L$
8. Time to platelet recovery in patients with CR or PR, defined as:
 - a. Number of days from Day 1 of commencing induction therapy to first day of platelets $50 \times 10^9/L$
 - b. Number of days from Day 1 of commencing induction therapy to first day of platelets $100 \times 10^9/L$
9. Rate of patients who become platelet transfusion-independent, defined as the proportion of patients who become platelet transfusion-independent based on the comparison of the PLT transfusion requirements in the 8 weeks prior to study Day 1 to the transfusion requirements in the 8 weeks following the last treatment course.
10. Rate of patients who become red blood cell (RBC) transfusion-independent, defined as the proportion of patients who become RBC transfusion-independent based on the comparison of the RBC transfusion requirements in the 8 weeks prior to study Day 1 to the transfusion requirements in the 8 weeks following the last treatment course.

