6 INVESTIGATIONAL PLAN

6.1 Overall design

This is an open label multicenter phase I/II study. Patients will be treated with venetoclax during 14 days in combination with AZA at 75 mg/m²/day for 5 days for each cycle or 50 mg/m²/day for 5 days each cycle if relapse occurred less than 4 months after allo SCT.

Patients who meet eligibility criteria will be administered VENETOCLAX orally at starting dose in phase I part and at MTD in phase II part on days 1-14 in combination with AZA at 75 mg/m²/day for 5 days on days 1-5 for each cycle or 50 mg/m²/day for 5 days each cycle if relapse occurred less than 4 months after allo SCT.

Following cycles must be administered on day 28 or delayed until day 42 in cases of hematological toxicity. Each cycle will last 28 days starting on day 1 of each cycle when ANC > 1 G/L and platelet > 50 G/L without transfusion or when recovery of baseline level.

In the phase I part, VENETOCLAX will be given once daily orally on days 1-14 for all cycles at escalating doses starting at Dose Level 1 (defined below) in combination with AZA +/- DLI. Patients will receive at least 8 cycles of VENETOCLAX/AZA/DLI unless progression occurs. Response will be assessed after 4, 6 and 8 cycles. Patients achieving a response (see appendix 11 and 12) will be able to continue on protocol with VENETOCLAX + AZA until 12 cycles maximum then with AZA alone. In the absence of response, patients will stop treatment.

Dose Levels for Treatment in Phase I

Dose Level	VENETOCLAX (mg)	Azacitidine (mg/m ²)
-1	50 mg*	75 (50 if relapse < 4 months)
1 (Starting dose)	100 mg*	75 (50 if relapse < 4 months)
2	200 mg*	75 (50 if relapse < 4 months)
3	400 mg*	75 (50 if relapse < 4 months)

*VENETOCLAX will be given once daily orally during 14 days.

In the phase II part, VENETOCLAX will be given once daily orally on days 1-14 for all cycles at MTD defined in the phase I part of the study in combination with AZA/DLI. Patients will receive at least 8 cycles of VENETOCLAX/AZA/DLI unless progression occurs. Response will be assessed after 4, 6 and 8 cycles. Patients achieving a response (defined below) will be able to continue on protocol with VENETOCLAX + AZA until 12 cycles maximum then AZA alone. In the absence of response, patients will stop treatment.

Ramp-up** will be performed at the beginning of cycle 1:

Dose Level	VENETOCLAX D1C1	VENETOCLAX D2C1	VENETOCLAX D3C1 and beyond
-1	10 mg*	20 mg*	50 mg*
1 (Starting dose)	20 mg*	50 mg*	100 mg*
2	50 mg*	100 mg*	200 mg*

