8.7 Follow-Up

Follow-up after treatment discontinuation for all patients.

Patients will be followed at 3 months and 6 months after treatment discontinuation. Date of death or last follow-up, disease status, and ongoing hematological treatments will be collected.

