24 APPENDIX

24.1 Appendix 1: VISIT SCHEDULE

	Screening ^a	Cycle 1					Cycle 2 and above ^b					End of Study ^c
Day	(-14 to 0)	1	7	15	21	28	1	7	15	21	28	
Visit	1	2	3	4	5	6	7	8	9	10	11	Final
Informed consent	X											
Demography and medical history	X											
Prior/concomitant medications ^d	X	X	X	X	X	X	X		X		X	X
Review inclusion/exclusion criteria	X											
Height/weight/body surface area calculation	X	X					X					X
Vital signs ^e	X	X	X	X	X	X	X		X			X
Physical examination ^f	X	X		X			X					X
ECOG performance status ^g	X	X		X			X					X
12-lead ECG	X			X			X					
CBC w/diff, platelets ^h	X	X	X	X	X	X	X	X	X	X	X	X
Comprehensive chemistry panel ⁱ	X	X	X	X	X	X	X		X		X	X
PT (INR) PTT	X	X					X					X
Complete urinalysis with microscopic exam	X											
Pregnancy Test ^j (if applicable)	X						X					
T/B/NK phenotype and Centralized biology	X						X				X ^l	X
Blood chimerism (CD3 sorted)	X						X					X
Medullar chimerism ^k	X										X	X
Adverse experience (AE) assessment		X	X	X	X	X	X		X		X	X
Dispense AZA		X					X					
Dispense VENETOCLAX		X					X					
Bone marrow aspirate /cytogenetics and for correlative studies ^l	X										X ^l	X

- a All pre-treatment studies should be obtained within 14 days of entry into the trial. Any abnormal results (except for bone marrow aspiration) should be repeated within 48 hours of beginning therapy to establish a baseline.
- b Patients may receive additional Cycles of therapy but not earlier than 4 weeks from the previous Cycle. One full cycle of treatment is defined as the administration of AZA and VENETOCLAX. During additional Cycles, patient Visits are numbered sequentially.
- c To be completed within 30 days of discontinuing study drug.
- d Medications will include the RBC and Platelet transfusions charts for the 8 weeks preceding inclusion and for the 8 weeks preceding beginning of AZA.
- e Vital signs to include temperature, pulse, respiratory rate and blood pressure.
- f A complete history and physical should be performed 48 hours before initiation of the study. A focused physical exam based on clinical assessment and AE evaluation should be conducted prior to the start of each Cycle.
- g See Appendix 5. ECOG should be performed within 48 hours of study initiation and then at the start of each Cycle.

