24.11.2 Partial remission (PR)

All of the CR criteria (if abnormal prior to treatment), except:

Bone marrow evaluation: Blasts decreased by $\geq 50\%$ over pretreatment but still > 5%. Cellularity and morphology are not relevant.

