24.12.2 AML response criteria

The following response criteria are based on the criteria of European LeukemiaNet (*Döhner et al*)[11].

CATEGORY	DEFINITION	COMMENT
Response		
CR without minimal residual disease (CR _{MRD})	If studied pretreatment, CR with negativity for a genetic marker by RT-qPCR, or CR with negativity by MFC	Sensitivities vary by marker tested, and by method used; therefore, test used and sensitivity of the assay should be reported; analyses should be done in experienced laboratories (centralized diagnostics)
Complete remission (CR)	Bone marrow blasts <5%; absence of circulating blasts and blasts with Auer rods; absence of extramedullary disease; ANC $\geq 1.0 \times 10^9/L$ (1000/ μ L); platelet count $\geq 100 \times 10^9/L$ (100 000/ μ L)	MRD ⁺ or unknown
CR with incomplete hematologic recovery (CR _i)	All CR criteria except for residual neutropenia (< $1.0 \times 10^9/L$ [1000/ μ L]) or thrombocytopenia (< $100 \times 10^9/L$ [100 000/ μ L])	
Morphologic leukemia-free state (MLFS)	Bone marrow blasts < 5%; absence of blasts with Auer rods; absence of extramedullary disease; no hematologic recovery required	Marrow should not merely be “aplastic”; at least 200 cells should be enumerated or cellularity should be at least 10%
Partial remission (PR)	All hematologic criteria of CR; decrease of bone marrow blast percentage to 5% to 25%; and decrease of pretreatment bone marrow blast percentage by at least 50%	
Treatment failure		
Primary refractory disease	No CR or CR _i after 2 courses of intensive induction treatment; excluding patients with death in aplasia or death due to indeterminate cause	Regimens containing higher doses of cytarabine (see Table 8 in [11]) are generally considered as the best option for patients not responding to a first

CATEGORY	DEFINITION	COMMENT
		cycle of 7+3; the likelihood of responding to such regimens is lower after failure of a first
Death in aplasia	Deaths occurring ≥ 7 d following completion of initial treatment while cytopenic; with an aplastic or hypoplastic bone marrow obtained within 7 d of death, without evidence of persistent leukemia	
Death from indeterminate cause	Deaths occurring before completion of therapy, or < 7 d following its completion; or deaths occurring ≥ 7 d following completion of initial therapy with no blasts in the blood, but no bone marrow examination available	
Response criteria for clinical trials only		

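### Three descriptive secondary endpoints in Protocol section 9.1 are loosely defined: blast response has no threshold, the transfusion window outruns scheduled data collection, and count recovery covers only patients whose response already requires it

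*Protocol*

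**What the plan says.** Section 9.1 of the Protocol lists, among the MDS secondary endpoints, "Rate of bone marrow blast response, defined as the proportion of patients with a reduction in bone marrow blast counts following treatment". No minimum fall, named marrow or baseline level is given. Elsewhere the Protocol sets a size: for PR, Appendix 11 (24.11.2) has "Blasts decreased by $\geq 50\%$ over pretreatment but still > 5" per cent, and marrow CR (24.11.3) also needs a fall of at least half. Section 6.1 states "Response will be assessed after 4, 6 and 8 cycles", so there are three scheduled response marrows, plus one at end of study.

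For AML, platelet and RBC transfusion independence compare the 8 weeks before Day 1 with the "transfusion requirements in the 8 weeks following the last treatment course". The visit schedule (Appendix 1) records concomitant medication up to the End of Study visit, which is "To be completed within 30 days of discontinuing study drug". Its footnote on medications names transfusion charts only for pretreatment periods. Section 8.11 lists blood product use as a safety assessment. For the 3- and 6-month contacts, section 8.7 says "Date of death or last follow-up, disease status, and ongoing hematological treatments will be collected".

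Also for AML, section 9.1 has "Time to neutrophil recovery in patients with CR or PR, defined as" the days from Day 1 to neutrophils of 0.5 and 1 × 10⁹/L. A parallel item covers platelets of 50 and 100 × 10⁹/L. In Appendix 12, CR requires ANC of at least 1.0 and platelets of at least 100 × 10⁹/L, and PR requires "All hematologic criteria of CR; decrease of bone marrow blast percentage to 5% to 25" per cent.

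**The concern.** A rule that accepts any fall in blasts picks up counting error as well as drug effect. A marrow reading that moves from 12% to 11.5% is a response. In a single-arm trial there is no control group to show how much of the resulting rate is noise.

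The transfusion endpoint needs 56 days of transfusion data after the last course, and the schedule does not clearly provide them. Late transfusions could go unrecorded, and a patient could then look independent.

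The recovery endpoint selects its patients on the outcome it describes. Patients with CRi (residual neutropenia or thrombocytopenia) and patients without a response are left out, so the result could be misread as showing that counts recover under the combination in general. Section 9.1 itself uses CR and CRi, not CR and PR, for AML overall response, duration of response and PFS.

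**Working it through.** The Protocol gives no rate, power or sample size for these endpoints, so there is no planned figure to reproduce.

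**Blast response.** Inputs: three response marrows (section 6.1) and 200 cells per marrow. The 200 is an assumption. It appears only in a comment on morphologic leukemia-free state in the AML table of Appendix 12, so 500 cells is used as a sensitivity case. Let the baseline reading B and a later reading F both be binomial(N, p) with the same p, meaning no true change.

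- One marrow: P(F < B) = (1 − P(F = B)) / 2. With N = 200 and p = 10%, P(F = B) = 0.0666, so P(F < B) = (1 − 0.0666) / 2 = 0.467.
- Any of three marrows: sum over b of P(B = b) × [1 − (1 − P(F < b))³], which gives 0.717 at p = 10%.
- Rule of at least 50%: replace F < B by F ≤ B/2.

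| True blasts (200 cells) | Any fall, one marrow | Any fall, any of three | ≥50% fall, one marrow |
|---|---|---|---|
| 5% | 45.4% | 70.3% | 7.9% |
| 6% | 45.8% | 70.7% | 5.8% |
| 8% | 46.3% | 71.3% | 3.1% |
| 10% | 46.7% | 71.7% | 1.7% |
| 15% | 47.2% | 72.3% | 0.3% |
| 20% | 47.5% | 72.6% | 0.1% |
| 25% | 47.7% | 72.8% | 0.01% |

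At 500 cells the any-fall figures are 47–49% and 72–74%. Without ties they would be 1/2 and 1 − 1/4 = 3/4, so the cell count hardly matters. Even with a true relative rise of 25% from 10–20% blasts, 10–19% of patients count as responders at one 200-cell marrow.

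If the analysis is limited to patients whose baseline reading is at least 5% (10 or more of 200 cells), the ≥50% rule gives 3.2% at true 8%, 7.4% at 6% and 13.0% at 5%. The rise at the low end comes from selecting high baseline readings. With any of three marrows the same three figures are 8.8%, 19.1% and 32.2%, which is a reason to name one marrow.

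**Transfusion window.** Venetoclax ends on day 14 of a cycle, so the latest End of Study visit is day 14 + 30 = day 44.

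- Window from day 14: 44 − 14 = 30 of 56 days covered (54%), 26 not.
- Window from day 28, the end of the cycle: 44 − 28 = 16 of 56 days covered (29%), 40 not.

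**Count recovery.** Set side by side, CR and PR both need ANC ≥ 1.0 and platelets ≥ 100 × 10⁹/L, and the endpoint's thresholds are 0.5 and 1 for neutrophils and 50 and 100 for platelets. Every analysed patient has met all four. The clock starts on Day 1, no earlier fall below the threshold is required, eligibility sets no upper limit on ANC or platelets, and a CBC is scheduled on Day 1. A patient who enters above a threshold therefore meets it on Day 1.

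**The case against.** The strongest reply is that little depends on these endpoints. None is listed in section 5.2, none has an analysis in section 10.2, and none enters the two-stage rule, the stopping rules or the sample size. CR, PR, marrow CR and HI are reported separately, and myelosuppression in all treated patients is covered by worst grades and shift tables. That stands, and it limits the point to descriptive results.

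On blast response, the 200-cell figure is borrowed from an AML comment, true blasts of 20% or more lie outside the MDS groups of Appendix 10, and the 70–73% figure needs all three marrows to be done and any one of them to count, which the Protocol does not state. The one-marrow figure needs none of the last and barely moves between 200 and 500 cells.

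A reader might infer that no transfusion data exist after the last course. The documents do not support that: the End of Study visit records medication and section 8.11 includes blood product use. Whether the hematological treatments collected at 3 and 6 months include transfusions is not stated. Reading independence after treatment instead of during it is also partly a choice of what to estimate.

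A reader might also infer that the recovery endpoint reports a 100% recovery rate or is meaningless. It is defined as a time among responders and can be described as such. CRi patients may have one lineage recovered.

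**Conclusion.** The point holds as a fault of definition in three descriptive secondary endpoints. The reading that they cannot measure benefit at all goes too far, and the primary decision is untouched.

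The blast-response definition is the clearest fault. With no true change it yields about 45–48% responders at one marrow and about 70–73% if any of three counts, for true blasts of 5–25%, 200 cells and binomial counting error only. The transfusion window is only partly covered, by at most 30 or 16 of 56 days depending on where it starts. The recovery endpoint gives timing among responders and must not be read as evidence that counts recover in all treated patients.

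**What to change.** Amend section 9.1 as follows.

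1. Define MDS blast response as a fall of at least 50% from the pretreatment marrow blast percentage, at one named scheduled response marrow, in patients with at least 5% blasts at baseline. With no true change, false response at one 200-cell marrow is then about 0.1–3% for true blasts of 8–20%, rising to about 7–13% at 5–6%. The cost is a lower reported rate and some overlap with the blast component of PR and marrow CR.
2. Define AML transfusion independence over an 8-week window that lies between Study Day 1 and the end-of-study visit, in patients transfused in the 8 weeks before Day 1, separately for RBC and platelets. This changes the quantity from the state after treatment to independence reached within the collection period. The medication footnote in Appendix 1 should name transfusion records for that period, since it now names only pretreatment charts.
3. Label time to neutrophil and platelet recovery as timing among CR or PR patients, state that it does not describe all treated patients, and do not count patients already above a threshold on Day 1 as recovering on Day 1.

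Items 1 and 3 are wording changes that use data already scheduled. Item 2 also needs the footnote change.
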